The goal of our project is to collect 1,200,000 speech samples from 2,000 people with dysarthria, where we expect to collect data from 400 people each from five different patient populations. Each person would provide 600 speech samples.

(600 samples/person x 400 persons/etiology x 5 etiologies = 1,200,000 samples)

Our schedule of research procedures is:

1. February or March-August 2023: data collection of speech samples from 400 people with Parkinson's. Parkinson's Disease is "etiology 1".
2. August 2023-August 2024: data collection of speech samples from 1,600 people with other etiologies to be determined (i.e., voted on by our Advisory Committee). One of these etiologies will be ALS. The other three etiologies are to be determined.

In Year 1, we focus on people with Parkinson's and therefore, recruitment will be managed by our partner the Davis Phinney Foundation, a well-known non-profit advocacy group for people with Parkinson's. DPF will distribute our recruitment flyer (see **Attachment 3, recruitment for speech**) and engage in informational sessions with potential participants. (In Year 2, we will do the same procedure for other populations of interest, such as ALS patients. Therefore, in Year 2, we will add additional patient advocacy organizations to assist in recruitment, such as Team Gleason to recruit patients with ALS.)

Data collection of speech samples in Year 1 will be a collaboration of UIUC and LSVT Global team members. Potential participants will be screened both with a questionnaire and by providing a short set of "quality control" speech samples (**Attachment 4**). If the participant does not pass screening, they will be thanked for their interest. Otherwise, the participant is eligible for the study and can do the informed consent process (**Attachment 5**) and then engage in contributing speech samples (**Attachment 7**).

Participants can do as many recordings as they wish at whatever time of day is convenient for them. Participants will be able to login to the system at any time, 24/7.

In Year 2, this procedure will be performed with patients from other etiologies with additional advocacy organizations as partners.

Participants also have the option to provide additional data about themselves, such as their age, race and ethnicity, year of their diagnosis, and other information as shown in **Attachment 9**. These "metadata tags" are completely optional but are helpful for analysis.

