9C. Describe additional safeguards included in the protocol to protect the rights and welfare of the populations selected above.

We have designed the remuneration plan to include support for caregivers.

Our subawards with DPF and LSVT Global are meant to provide extra support for potential participants. DPF's recruitment activities include providing information and support as needed to potential participants to answer their questions. If a potential participant does not seem able to provide informed consent, they will not be recruited. LSVT Global will provide an intake coordinator and a number of mentors to support data collection. We anticipate that many participants will need advice and support during their attempts at data collection online, and so they will be able to schedule time with an LSVT Global mentor to get help.

Section 10. INCLUSION/EXCLUSION

10A. List specific criteria for inclusion and exclusion of subjects in the study, including treatment and control groups.

For the main study to collect speech samples, total n=2000 where Cohort 1 (n=400) etiology is Parkinson's Disease, and Cohort 2 etiologies are still to be decided (n=1600) for Year 2.

Inclusion criteria:

- Adult (age \geq 18 years)
- Self-reported diagnosis of Parkinson's Disease or other etiology of interest
- Reads and speaks English
- Has a valid email address
- Ability to access web browser to participate in study

Exclusion criteria:

- Is a resident of the State of Washington, Texas, or Illinois (because these states have privacy laws that would not allow us to collect 'voice prints')
- If quality control screening of initial speech samples "fails" because of poor data quality (e.g., poor quality recording environment, or person's speech is "too typical" and not sufficiently interesting to continue collecting)

10B. Explain how the inclusion/exclusion criteria will be assessed and by whom. If special expertise is required to evaluate screening responses or data, list who will make this evaluation and describe their training and experience.

Assessing the inclusion/exclusion criteria will be in collaboration with patient advocacy organizations. In Year 1, that will be Davis Phinney Foundation and LSVT Global.

10C. Drafts or final copies of all screening materials are attached. Yes Not Applicable

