**14A. Indicate all that apply for the consent/assent/parental permission process.**

Written informed consent (assent) with a document signed by
 adult subjects parent(s) or guardian(s) adolescents aged 8–17 years

Waiver of Documentation (signature) of Informed Consent (*include the relevant [Waiver Form](#)*)
 adult subjects parent(s) or guardian(s) adolescents aged 8–17 years

Waiver of Informed Consent (*include the relevant [Waiver Form](#)*)
 adult subjects parent(s) or guardian(s) adolescents aged 8–17 years

Alteration of Informed Consent (*include the relevant [Alteration Form](#)*)
 adult subjects parent(s) or guardian(s) adolescents aged 8–17 years

14B. List all researchers who will obtain consent/assent/parental permission from participants.

DPF personnel will publicize the opportunity to their clients and offer support as needed, such as group information sessions and one-on-one dialog.

14C. Describe the method for obtaining consent/assent/parental permission.

The consent procedure will be conducted online with optional support as needed. DPF will generate many referrals of potential participants who self-report that they meet initial inclusion criteria. These referrals will be kept as a list of names and email addresses that are shared with LSVT Global and UIUC. LSVT Global's intake coordinator will contact each potential participant to verify their information and ensure that they provide the quality control samples of their speech in the online UIUC system. UIUC personnel will assess these two pre-screening data sources (initial questionnaire and quality control samples) and decide whether or not the participant is eligible. If not, then the participant is thanked for their interest. If the person is eligible, then the person's information is confirmed with LSVT Global and the person is directed to the online informed consent document with the option to get help. While it is possible for the person to read and sign the online informed consent document and immediately begin data collection through the UIUC online system all by themselves, it is more likely that the LSVT Global intake coordinator will schedule time with an LSVT Global mentor or UIUC research team member to talk the person through the informed consent document and help them with the first few sessions of data collection.

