Recruitment flyer for participants to contribute data

Your voice is needed to improve speech technology!

Intelligent devices can understand spoken commands because they've been trained using millions of hours of audiobooks and radio broadcasts. If you have a speech impairment, though, your devices probably don't understand you so well. The Speech Accessibility Project wants to record examples of your speech, so that researchers and companies can improve their devices so that they work better for you.

Mission Statement: The goal of the Speech Accessibility Project is to improve speech technologies for all people, by collecting speech data and sharing it with technology partners.

How it works: You use a web browser to access our system 24/7, where you will be prompted to provide audio samples of your speech, either by reading a sentence or answering a question. You can provide speech samples at your own pace and on your own schedule.

Compensation: You can earn up to \$180 for contributing 600 verified samples to the system. If you need a caregiver to help you participate, your caregiver can earn up to \$90 as well.

About us: The Speech Accessibility Project is managed at the University of Illinois Urbana-Champaign, is funded by a consortium of technology companies (currently Amazon, Apple, Google, Meta, and Microsoft), and is partnered with the Davis Phinney Foundation and LSVT Global advocacy organizations. The leader of the Speech Accessibility Project is [name] at UIUC.

How to get started: You can sign up at our website (<https://speechaccessibilityproject.beckman.illinois.edu>) or contact our recruitment team at the Davis Phinney Foundation at ([contact]).

For more information, visit <https://speechaccessibilityproject.beckman.illinois.edu/about-the-project>.

NOVA H Attachment 4: Participant Pre-Screening for Speech Samples

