Initial pre-screening will be conducted with a combination of online and live engagement with potential participants. There are two parts to the pre-screening: Step 1 is a short questionnaire and Step 2 is providing a set of quality control speech samples. The questionnaire may be answered online by the potential participants directly (via a URL that is shared with them via email and is not public) or may be conducted as a telephone or Zoom interview with a member of the research team. Therefore, the Step 1 Pre-Screening Questionnaire shown below will be implemented both as an interactive web page and as an interview script.

Step 1: Pre-Screening Questionnaire

Thank you for your interest in the Speech Accessibility Project! To help us determine whether we can record your voice, please answer a few questions about yourself.

The information provided in these pre-screening questions will only be used to confirm your eligibility in the study and will remain confidential. This information will not be shared outside of the UIUC research team.

- 1. Do people or devices (e.g., Alexa, Siri) have a hard time understanding your speech?**
<Answer field: Menu options Yes or No>
- 2. Have you been diagnosed with Parkinson's Disease?**
<Answer field: Menu options Yes or No>
- 3. Are you 18 years of age or older?**
<Answer field: Menu options Yes or No>
- 4. What state do you live in?**
<Answer field: Drop-down menu listing all U.S. states, and the option "None of the above">
- 5. Do you have a valid email address?**
<Answer field: Menu options Yes or No>
- 6. Do you have regular access to a web browser?**
<Answer field: Menu options Yes or No>
- 7. Do you have the ability to read and speak English?**
<Answer field: Menu options Yes or No>

Note: ANSWER 1 and ANSWER 2 can be any answer; this is useful information but not screening criteria.

IF ALL OF THE FOLLOWING CONDITIONS ARE TRUE:

ANSWER 3 = Yes

ANSWER 4 = any state except IL, TX, WA, "none of the above"

ANSWER 5 = Yes

ANSWER 6 = Yes

ANSWER 7 = Yes

THEN CONTINUING: "Thank you! So far it looks like you are eligible to be in the study."

ELSE FAILED PRE-SCREENING: "We're sorry. It looks like you are not eligible to be in our study. Thank you for your interest. Please stay in touch with us at <https://speechaccessibilityproject.beckman.illinois.edu>"

IF CONTINUING, go to STEP 2 below. The text below is both on a web page and used as telephone/Zoom script by a member of the research team.

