Step 2: Quality Control Speech Samples

Thank you! So far, it looks like you are eligible to be in our study. To confirm your final eligibility, the next step is for you to provide us some examples of your speech. We will give you access to a website where you will be prompted to record a small number of sentences (about 20 sentences). After you establish a login and password, the website will present you with a text prompt and the capability to record and save your speech samples. Your task is to make a set of voice recordings. The system will prompt you to read some text, and you will record yourself reading that text aloud. You can quit at any time and come back to this task later.

This task is performed entirely online at your own convenience. You may stop this task and restart it at any time at your own convenience, 24/7. You do not need to make all the recordings in one session; you can feel free to perform this task for just a minute or two each day spread over one week. We estimate that this task will take about 10 minutes of your time in total.

After you have submitted the full set of speech samples, the UIUC research team will evaluate the quality of your recordings. Within one week, the UIUC research team will contact you to either confirm that you may continue to participate in the study, to work with you to improve your recording environment, or to let you know that you will not be asked to participate any further in this study.

If you **are not** eligible to be in the study based on your speech samples, we will delete all of your data including your email address.

If you **are** eligible to participate in the study based on your speech samples, the speech samples provided for pre-screening will only be used to confirm your eligibility in the study, will remain confidential, and will not be shared outside of the UIUC research team.

Go to **this website** (<<insert URL here>>). If you need help to provide these samples or have any questions, please contact (<insert name, email, telephone number of research team member>).

"This website" will include the following text:

Welcome to the Speech Accessibility Project pre-screening website! At this site, you will be prompted to record a small number of sentences (about 20 sentences) that our research team will analyze in order to make sure that you are eligible to participate in our study.

First, please establish a login and password.

<Login and password process>

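### Does excluding people for a poor recording environment conflict with the offer to help fix it, and must rejections be counted by reason before data are deleted?

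*Combined protocol and SAP*

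**What the plan says.** Section 10A lists failure of quality-control screening as an exclusion, on grounds of poor data quality. Its examples are "poor quality recording environment, or person's speech is 'too typical' and not sufficiently interesting to continue collecting".

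Section 7F says that screening consists of a questionnaire and a short set of speech samples, and refers the reader to Attachment 4. The next sentence but none intervening reads: "If the participant does not pass screening, they will be thanked for their interest". Section 14C gives the decision to the university team ("UIUC personnel will assess these two pre-screening data sources") and also ends in two outcomes: the eligible go on to consent, and for the rest, "If not, then the participant is thanked for their interest".

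Attachment 4, Step 2, lists three things the team may tell an applicant within one week: that they may continue, that the team wants "to work with you to improve your recording environment", or that they will not be asked to take part further. The pre-screening website text repeats all three. Both say that anyone found ineligible on their samples will have all their data deleted, email address included.

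On records, 14C says of people referred by the Year 1 recruitment partner: "These referrals will be kept as a list of names and email addresses that are shared with LSVT Global and UIUC". The recruitment flyer gives another way in: "You can sign up at our website". In Attachment 4, Step 1, the questions on speech difficulty and on a Parkinson's diagnosis carry the note "this is useful information but not screening criteria". Section 10D relies on optional demographic answers from participants to judge how well the sample represents people.

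**The concern.** There are two strands.

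First, 10A makes a poor recording environment a ground for exclusion, and 7F and 14C name only pass or thank-you. Attachment 4 adds a middle course, and no sentence says that help comes before exclusion or whether the person may record again. Staff working from 10A, 7F and 14C alone could turn away someone whom Attachment 4 had led to expect possible help.

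Second, 10A puts a correctable feature of the room and a property of the speaker under one heading. If rejections are not split by reason and the data are then deleted, the project could not later say whether it had selected on atypical speech, which is its stated target in section 6A, or on home recording conditions. The records that are described do not fill this gap. The referral list holds names and email addresses without reasons, website sign-ups may not be on it, and the 10D check covers only people who enrolled. A bare total would also include people without a Parkinson's diagnosis, since that answer does not stop anyone from reaching Step 2.

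What would be at stake is who is represented in the database. No treatment effect or comparison is involved.

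**Working it through.** **1. The planning figure.** Section 7F gives 600 samples per person, 400 people per etiology and 5 etiologies. 600 × 400 × 5 = 1,200,000 samples, and 400 × 5 = 2,000 people. Both match the plan. These are enrolment targets, so screening failures do not enter them.

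**2. The texts side by side.**

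| Place | Outcomes described | Nature of the text |
|---|---|---|
| 10A | Excluded if screening fails | Criterion |
| 7F | Pass, or thanked | Summary that cites Attachment 4 |
| 14C | Eligible, or thanked | Final decision |
| Attachment 4, Step 2, and website | Continue, improve the environment, or no further part | Contact within one week of submission |

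The 7F sentence on thanking people directly follows the one that defines screening by reference to Attachment 4, so 7F takes in the three-way contact. Working on the recording environment is not an end state: afterwards the person is either eligible or not, which is the pair of outcomes in 7F and 14C. Section 10A applies once screening has failed, and someone still being helped has not yet failed. All four texts fit one sequence: record, receive help if the environment is the problem, then decide. Attachment 4 makes help one of three alternatives and does not guarantee it to everyone, so a rejection without help breaks no stated commitment.

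**3. How many people could be affected.** The documents state no failure rate, so f below is an assumption, as is enrolment of everyone who passes. Number screened = 400/(1 − f), rounded up; number rejected = screened − 400.

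| Assumed f | Calculation | Screened per etiology | Rejected per etiology |
|---|---|---|---|
| 10% | 400/0.90 = 444.4 | 445 | 45 |
| 20% | 400/0.80 = 500 | 500 | 100 |
| 40% | 400/0.60 = 666.7 | 667 | 267 |

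For all 2,000 people, 2,000/(1 − f) gives 2,223, 2,500 and 3,334 screened, so 223, 500 and 1,334 rejected. With no count by reason, the share due to recording quality could lie anywhere from 0% to 100%. That is true of any unrecorded split, so it describes what is unknown and is not evidence of a skew.

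**4. What a count by reason would show.** The natural Year 1 table is Parkinson's yes or no (the only etiology question in Step 1) by three outcomes (pass, recording quality, speech too typical): 2 × 3 = 6 cells. It would show why people were screened out. It would not show whether rejections fell unevenly by age, race, sex or income, because Step 1 asks for none of these beyond a yes or no on being 18 or older. In Year 1 there is one target etiology, so it could not compare target groups either. A No to the Parkinson's question may mean another condition or none.

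**The case for a change.** The strongest opposing case is that nobody has written the sequence down. Attachment 4 speaks to applicants, whereas 10A is the eligibility rule, and a staff member may apply the rule as printed. The mentor support in 9C concerns data collection and is not set as a step before rejection. Reasons not noted before deletion cannot be reliably rebuilt, and an anonymous aggregate count would leave the deletion safeguard intact for little effort.

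Much of this stands as description. The order of help and exclusion is unstated, and no visible text describes a tally. It is also unclear whether a rejected person stays on the referral list, since 14C says the list is kept and Attachment 4 says the email address is deleted.

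The step from there to a needed change does not stand. The people who make the decision under 14C are on the university team, the same team that Attachment 4 says will evaluate the recordings and contact the applicant, so they work with the three-outcome text. Deleting personal data does not prevent anyone from counting outcomes, and silence in the visible text, part of which was removed, does not show that nobody will. The count would also require rewording a pre-consent assurance that screening information serves only to confirm eligibility, in return for a table that cannot answer the question about representation. A skew among those enrolled could still appear in the 10D data, subject to optional answers; what would stay hidden is its cause. Whether a No on diagnosis should stop someone at Step 1 is a separate matter, and 14C puts the questionnaire and the samples before the same decision-makers.

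**Conclusion.** No change follows. The apparent conflict is an unstated sequence that staff can fill sensibly from Attachment 4, to which 7F already points. If the plan is followed as written, including the text shown to applicants, people with a poor recording environment may be helped before a final decision, and no result becomes wrong. The missing count is an optional record. It would let the project report why people were screened out, but it would not reveal demographic skew, and it corrects no rule or figure in the plan.

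The size of any selection cannot be stated from the documents; the illustrative 45 to 267 rejections per etiology rest wholly on assumed failure rates of 10% to 40%. The conclusion assumes that working on the recording environment is an interim step and that the removed pages do not say otherwise. A sponsor revising these sections for another reason could add a clause on the order of help and exclusion, but nothing in the study depends on it.

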10D. Describe procedures to assure equitable selection of subjects. Justify the use of the groups marked in Section 9B. Selection criteria that target one sex, race, or ethnic group require a clear scientific rationale.

We will offer participants the optional ability to provide demographic data, so that we can assess the diversity and equitable representation of our sample.

Section 11. RECRUITMENT

11A. Select all recruitment procedures that will be used.

- Student subject pool, *please specify*:
- Email distribution
- MTurk, Qualtrics Panel, or similar online population, *please specify*:
- US Mail
- Flyers/brochures
- Website ad, online announcement (e.g. eWeek), or other online recruitment, *please specify*: newsletter announcements via organizations that advocate for and support people with disabilities.
- Newspaper ad
- Verbal announcement
- Other, *please specify*:
- Not applicable (secondary data only)

11B. Drafts or final copies of all recruitment materials (including verbal scripts) are attached.

Yes Not Applicable

11C. For each group of participants, describe the details of the recruitment process.

In Year 1, Davis Phinney Foundation will include our recruitment flyer in their distribution channels, will also host optional information and Q&A sessions with potential participants, and will answer individual questions as needed from potential participants. The UIUC Speech Accessibility Project's website will remain as a public source of information, including an updated FAQ list that may be updated based on feedback from DPF.

Section 12. REMUNERATION AND PLAN FOR DISTRIBUTION

Refer to the University [Business and Financial Policies and Procedures](#) for further guidance on the compensation process and reporting requirements.

12A. Will subjects receive inducements or rewards before, during, or after participation?

Yes No

If yes, complete the rest of Section 12. If no, proceed to Section 13.

12B. Select all forms of remuneration that apply.

- Cash, *please specify amount*:

Check, please specify amount:
 Gift Certificate, please specify amount: Amazon ecodes adding up to \$180 per data contributor and up to \$90 per caregiver.
 Lottery, please specify amount: and odds:
 Course Credit, please specify amount: and specify equivalent alternative activity:
 Other, please specify:

12C. Will payment be prorated before, during, or after participation?

Yes, please specify how: prorated by number of recorded sentences uploaded to our system

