 No

12D. For each group of participants, describe the details of the remuneration plan, including how, when and by whom they will be notified.

Our project plans to obtain a total of 600 recorded sentences per participant. Each participant will be compensated with up to \$180: \$60 after recording the 200th sentence, an additional \$60 after recording their 400th sentence, and an additional \$60 after recording their 600th sentence.

In addition to the participant compensation described above, participants will also be able to name a caregiver who is assisting them with performing the computer usage tasks in this study, and to specify additional compensation to the caregiver. Named caregivers will be compensated with up to \$90: \$30 after recording the 200th sentence, an additional \$30 after recording their 400th sentence, and an additional \$30 after recording their 600th sentence.

The NOVA H customized database system will track number of sentences per participant that are uploaded. The database will have a regular schedule of quality control checks and a built-in alert to remind the NOVA H project manager that payments are due as appropriate. The NOVA H project manager will then use the usual UIUC procedure to compensate the participants via automated email messages containing an appropriate Amazon ecode.

The Beckman Institute is fully aware of OBFS guidance on potential IRS tax implications of human subject payments. The NOVA H project manager will assure that the team follows OBFS guidance and will work closely with the Beckman business affairs office to ensure that tax implications are addressed.

12E. The information listed above is provided on the relevant consent forms.

Yes

Section 13. RISKS & BENEFITS

13A. Describe all known risks to the participants for the activities proposed, such as risks to the participants' physical well-being, privacy, dignity, self-respect, psyche, emotions, reputation, employability, and criminal and legal status. Risks must be described on consent forms.

Risks include (1) the risk of loss of privacy in case any research institution that has been granted data access violates their data use agreement by releasing participant speech samples to people not covered by the agreement, and (2) the risk that subjects may get tired while recording sentences.

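### Does counting recordings as uploads in 12C and 12D, but as verified samples in the flyer, call for a change to the plan?

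*Combined protocol and SAP*

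**What the plan says.** Section 12C prorates payment by uploads: "prorated by number of recorded sentences uploaded to our system". Section 12D begins with the target ("Our project plans to obtain a total of 600 recorded sentences per participant") and sets three equal steps, at the 200th, 400th and 600th recorded sentence. Each step is worth $60 to the participant and $30 to a named caregiver, so the maxima are $180 and $90, as in 12B.

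12D then describes how payment runs. First, "The NOVA H customized database system will track number of sentences per participant that are uploaded". The database will also have "a regular schedule of quality control checks and a built-in alert to remind the NOVA H project manager that payments are due". The project manager then sends the gift codes by email.

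The recruitment flyer gives the same maxima but words the target differently: up to $180 "for contributing 600 verified samples to the system". It lists no intermediate steps. The available text does not define verified. Section 12E says that the consent forms carry the payment terms; those forms were not in the copy reviewed.

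**The concern.** The count of recordings decides when money is due, and it is described in two ways. An upload exists once the file is in the system; a verified sample has presumably passed a check. Quality checks are planned, so some recordings could fail. 12D does not say whether a failed recording leaves the count or may be recorded again.

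Because payment is stepped, a difference of one recording can cost a whole step. A participant who read the flyer and one who was told the terms of 12D might then expect different amounts for the same work. At stake are fair treatment of participants and agreement between recruitment material and the approved procedure. These matter even where no analysis is involved.

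**Working it through.** **Inputs.** Steps at 200, 400 and 600, worth $60 (participant) and $30 (caregiver): 12D. Planned recordings per person, 600: 12D and 7F. Number rejected: not given, so treated as an assumption.

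**The plan's own figures.** For n counted recordings and step value s, up to n = 600 and beyond:

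pay(n) = s × min(3, floor(n / 200))

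At n = 600 this is 3 × $60 = $180 and 3 × $30 = $90, as 12B, 12D and the flyer state. The collection target in 7F also reproduces: "600 samples/person x 400 persons/etiology x 5 etiologies = 1,200,000 samples".

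**One rejected recording, not replaced.** The upload count uses u and the verified count uses u − 1. The flyer states no steps, so applying those of 12D to verified samples is an assumption.

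| Uploads | Verified | Participant: uploads / verified | Caregiver: uploads / verified |
|---|---|---|---|
| 200 | 199 | $60 / $0 | $30 / $0 |
| 400 | 399 | $120 / $60 | $60 / $30 |
| 450 | 449 | $120 / $120 | $60 / $60 |
| 599 | 598 | $120 / $120 | $60 / $60 |
| 600 | 599 | $180 / $120 | $90 / $60 |
| 601 | 600 | $180 / $180 | $90 / $90 |

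From 1 to 600 uploads, a single rejection changes the amount only at 200, 400 and 600.

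**More rejections at 600 uploads.** With 1 to 200 rejected, the verified count is 599 to 400 and pays $120, so the gap stays at $60 (caregiver $30). With 201 rejected the count is 399 and the gap is $120 (caregiver $60).

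**If rejected recordings are replaced.** The final amount is the same under both counts; only the number of recordings differs. At assumed rejection rates of 1%, 5% and 10%, 600 verified samples need 600 / 0.99, 600 / 0.95 and 600 / 0.90 uploads, which round up to 607, 632 and 667. Section 7D allows up to 5 hours for training and 600 samples, so at most 300 min / 600 = 0.5 min per recording on average. The extra time is then about 7 × 0.5 = 3.5 min, 32 × 0.5 = 16 min and 67 × 0.5 = 33.5 min.

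**Can the texts be read together?** 12D runs in this order: uploads are tracked, quality checks are scheduled and an alert says payment is due, and the project manager pays. If verified means an upload that has passed those checks, the flyer describes the end of the same process. 12D does not say this outright, but nothing in it rules it out. Section 7F also lets participants record as much as they like at times they choose. That may be meant only as a statement about pacing, but it sets no ceiling that would bar a replacement.

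**The case for a change.** The strongest case for a change is that payment terms are a promise, and the flyer is what recruits see first. The planned stopping point for everyone is 600, which is exactly a count at which one rejection matters, so the example is the planned case and not a rarity. Failed recordings are also foreseeable: the exclusion criteria in 10A and the pre-screening in Attachment 4 both deal with poor recordings. If 12E holds, the same loose wording may be repeated in the consent form. One agreed term would cost little.

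Much of this stands. The wording does differ, verified is undefined, and the rule for failed recordings is unwritten. Three things weaken the step from there to a needed change.

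- The loss requires that a person at 600 uploads is refused one more recording. No visible section says so.
- The explicit pass or fail decision is made at pre-screening, where staff may also help to improve the recording environment. No visible section describes rejecting individual main-study recordings for payment, and the sample prompts in Attachment 7 tell participants that mistakes are acceptable.
- The flyer gives a ceiling, not a schedule. The $120 figure comes from joining the flyer's unit to the steps of 12D, a rule that neither document states.

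The consent forms may settle the matter either way, so their content cannot support a finding.

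**Conclusion.** The inconsistency is real but minor, and it does not call for a change to the plan. At worst, a participant who stops at exactly 200, 400 or 600 uploads with one rejected and unreplaced recording is one step short: $60, and $30 for a named caregiver. If replacement is allowed, payment is only delayed. The shortfall rests on three assumptions: that the steps of 12D apply to verified samples, that individual recordings are rejected for payment, and that they cannot be replaced. The documents state none of these.

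Settling on one term would read better, but it would alter no planned number, estimate, safety provision or source of bias. In the available text nothing is computed from the payment count; the 1,200,000 in 7F is a collection target at full completion and stays the same under either word. A project manager following 12D has a workable order of upload, check and pay, and the database would be sound if the plan were carried out as written.
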